6.3.5 Heparin Anticoagulation therapy

- ❖ Heparin is a naturally occurring anticoagulant that binds to the enzyme inhibitor antithrombin III (AT-III) causing a conformational change which results in its active site being exposed. The activated AT-III then inactivates thrombin and other proteases involved in blood clotting, most notably factor Xa.
- ❖ 1000 units of heparin will be used as a loading dose with a maintenance dose of 1000U heparin/hr via the heparin infusion port, with the syringe on the 2008T machine.
- ❖ The heparin dose may be adjusted to the patient's stable dialysis regimen.

6.3.6 Sampling

Blood samples will be drawn from sampling sites along the extracorporeal blood circuit. Ionized calcium samples will be drawn from extracorporeal blood circuit before citrate infusion site.

6.3.7 Required Support Equipment for SCD Treatment

(Refer to individual equipment manual for proper operating instructions.)

6.3.8 Operating SCD Circuit During Normal Treatment Period

Observe pressure monitors for any consistent, large pressure fluctuations (this could indicate a clotting problem or line occlusion). If the problem persists, call the Principal Investigator. If pressure build up is such that Circuit lines could fail, SCD therapy will be discontinued immediately.

6.3.9 Conclusion of Normal SCD Perfusion

At the conclusion of SCD therapy the patient's blood in the SCD system will be returned to the patient under conventional dialysis and hemodialysis treatment procedures.

6.3.10 Removal of the SCD

After the conclusion of SCD therapy the SCD circuit system will be flushed by research personnel with normal saline to clear the SCD cartridge of residual blood. Elution buffer will be infused into the cartridge and all ports capped.

6.3.11 Discontinuation of SCD Therapy Due to Adverse Event

If the Principal Investigator or Principal Investigator delegate determines that SCD therapy should be discontinued prior to the scheduled end of treatment, the following procedure should be followed:

- A. The dialysate pump system is turned off.
- B. A decision to return the blood in the extracorporeal blood circuit to the patient is made.
- C. The SCD and its circuit are removed from the dialysis system.
- D. The PI decides to reinstate hemodialysis.

If there is clotting of the cartridge per se unaccompanied by any clinical prohibitions, the clotted cartridge is to be removed and replaced with a new device. See section 6.3.14 below.

6.3.12 Warnings and Precautions

The following warning and precautionary signs could indicate potential system failures:

- A. Changes in patient status should be referred to the clinical investigator.
- B. Any leakage of blood from system lines.
- C. Any sudden large (>40%), persistent (>2 minutes) change in monitored pressures.
- D. Air observed in lines.

- E. Development of clots in bubble traps or SCD cartridge extracapillary space.

6.3.13 Required Documentation

The following items need to be recorded:

- A. Time of SCD cartridge hook-up.
- B. Time of SCD system integration with hemodialysis system.
- C. Visual inspection of SCD system upon initiation of perfusion.
- D. Calcium levels in blood samples and other parameters as required during Citrate anticoagulation therapy per University of Michigan protocol.
- E. System pump speeds every hour.
- F. Adjustments in IV pump infusion rates.
- J. Time of cessation of SCD therapy.
- K. Any unanticipated occurrences should be recorded in hourly comment sections.

6.3.14 Hemodialysis Cartridges

A new SCD cartridge will be used for each treatment.

In the event that either hemodialysis cartridge is not usable for the entire treatment for any reason, a new cartridge will be placed within the perfusion circuit using procedures similar to replacing cartridges during standard hemodialysis.

6.3.15 Dialysis Prescription

- ❖ Subjects will have their routine hemodialysis treatment with the added SCD filter.
- ❖ All “chronic hemodialysis treatments” will be conducted according to usual clinical practice, using standard hemodialysis machines.
- ❖ The schedule of chronic dialysis will be consistent with the research subjects’ routine treatment day.

- ❖ The Principal Investigator will adjust net ultrafiltration to achieve the patient's established stable dry weight.

6.3.16 Duration of Treatment

Each Subject will receive one SCD treatment.

6.3.17 Disconnecting From the SCD Cartridge

- ❖ All blood in the Study Hemofiltration Circuit will be returned to the Subject (unless contraindicated due to presence of clot, Subject's volume status, etc.).
- ❖ If the access being used is a tunneled catheter, flush each lumen with 10 mL of 0.9% NaCl solution USP and then instill a heparin flush (5,000 units/mL) into the ports.
- ❖ If the access being used is an AV fistula or AV graft, remove the dialysis needles or vascular catheters (i.e. angiocaths) used to cannulate the access according to the hospital's dialysis unit protocol.

7. Concomitant Therapy

7.1 Permitted Medications and Therapies

The Subject should continue receiving his usual chronic medications during the Study without limitation in addition to any other needed medications. Routine medications will be given after SCD treatment.

8. Study Methods

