8.3.1 Study Treatment

Each Subject will have the treatments described below, during which identical study procedures will be performed during each study treatment.

Treatment 1: Initial standard hemodialysis treatment with heparin (SHH) anticoagulation.

Treatment 2: A single hemodialysis treatment with SCD treatment and regional citrate anticoagulation one week after Treatment 1.

Each subject's safety data will be monitored by the PI on an ongoing basis.

Prior to start of Study Treatment (SHH or SCD Treatment)

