8.3.1.1 Perform 2 D echo

8.3.1.2 Prepare a heparin or citrate intravenous infusion per hospital routine to use with a standard volumetric programmable pump and Crit-Line III online hematocrit measurement device if required by the citrate protocol.

- 8.3.1.3 Assemble blood drawing supplies, including ice bucket, and label tubes.
- 8.3.1.4 Assemble and set-up Study Circuit.
- 8.3.1.5 For Subjects with AV fistula or graft, access with needles or venous cannula (i.e., angiocatheters) according to Investigator orders or per hospital routine.
- 8.3.1.6 For Subjects with tunneled catheters, aspirate heparin flush according to Investigator orders or per hospital routine.
- 8.3.1.7 Review medical history.
- 8.3.1.8 Review concomitant medications.
- 8.3.1.9 Obtain BP, RR, and HR, weight without shoes or over clothes, and oral temperature. Perform physical exam.
- 8.3.1.10 Obtain blood for albumin according to instructions in **Appendix 2**.
- 8.3.1.11 Obtain blood for basic metabolic panel according to instructions in **Appendix 2**.
- 8.3.1.12 Obtain blood for CBC with differential and platelets according to instructions in **Appendix 2**.
- 8.3.1.13 Obtain blood for systemic soluble markers according to instructions in **Appendix 2**.
- 8.3.1.14 Obtain blood for flow cytometry according to instructions in **Appendix 2**.

Initiate the Study Hemodialysis Treatment (SHH or SCD Treatment)

- 8.3.1.15 Begin intravenous heparin infusion as prescribed by standard protocol (*for SHH treatment, heparin will be used for the entire duration of the procedure. For the SCD treatment, heparin will be used only during the first hour of the SCD treatment.*)
- 8.3.1.16 Turn on blood pump at the speed prescribed by the Principal Investigator. Turn on the calcium infusion per protocol.
- 8.3.1.17 Obtain BP, HR, and RR.

Repeated Procedures During Entire Study Hemodialysis Treatment (SHH or SCD Treatment)

- 8.3.1.18 Record Adverse Events.
- 8.3.1.19 Record concomitant medications.
- 8.3.1.20 Adjust heparin flow rate as needed for SHH or calcium chloride administration rate for SCD treatment protocol to maintain systemic iCa level between 1-1.3 mM during the citrate anticoagulant therapy. Document the pre-SCD filter ionized Ca as required.
- 8.3.1.21 Observe cartridges for evidence of hemolysis, clotting, and leakage hourly.

At 1 Hour into Study Treatment Protocol (For SCD Treatment Only)

- 8.3.1.22 Obtain blood for iCa with i-STAT, a bedside diagnostic device (Abbott Labs).

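### Section 7.1 times routine medications around the SCD session only, so drug timing may differ between the two sessions compared within each patient

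*Combined protocol and SAP*

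**What the plan says.** Section 7.1 of the combined protocol and SAP has two parts. Subjects keep taking their "usual chronic medications during the Study without limitation", and any other needed medication is allowed. It then adds one timing rule: "Routine medications will be given after SCD treatment".

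Section 8.3.1 defines two sessions. Treatment 1 is standard hemodialysis with heparin. Treatment 2 is "A single hemodialysis treatment with SCD treatment and regional citrate anticoagulation one week after Treatment 1". The same section says that "identical study procedures will be performed during each study treatment". The listed procedures that concern medication are 8.3.1.8 before the session ("Review concomitant medications") and 8.3.1.19 during it, which asks for concomitant medications to be recorded.

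Section 6.3.15 says that chronic hemodialysis treatments "will be conducted according to usual clinical practice, using standard hemodialysis machines". Sections 8.4.1 and 9 make each patient his or her own control, heparin session against SCD session.

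**The concern.** In a two-session comparison within patients, anything that changes systematically with the session becomes part of the estimated treatment difference. Here the order is fixed, so there is no second sequence in which such a change could balance out. A medication rule that applies to one session only can create this kind of change.

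The outcome measures make drug timing relevant. Section 8.4.1 chooses regional wall motion and global longitudinal strain because they depend less on preload and afterload than other parameters, but it says the dependence is not removed. Section 1 links myocardial stunning to intradialytic hypotension, and criterion 5.1.8 admits patients prone to it. As an illustration only, take a patient who normally uses a blood-pressure-lowering drug before dialysis. Read literally, the plan leaves that dose in place for the heparin session and defers it for the SCD session. A difference in wall motion between the sessions could then reflect the drug, the device, or both.

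**Working it through.** No arithmetic applies. The plan gives no figure on this point, and the remedy leaves the sample size at 10. The check is a reading of the text.

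1. **What does SCD treatment mean in 7.1?** Section 6.2 describes it as treatment with the two-cartridge system. Section 6.3.16 says "Each Subject will receive one SCD treatment", while every patient has two study sessions. Section 8.3.1.15 sets the two apart: heparin runs throughout the SHH session, but "For the SCD treatment, heparin will be used only during the first hour". The subheadings in 8.3.1 name SHH and SCD together when both are meant. On this usage the rule in 7.1 covers Treatment 2 only.

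2. **Does any other text time routine drugs on the heparin day?** None was found. The general part of 7.1 lets usual drugs continue without a time, and 6.3.15 refers to usual practice.

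3. **Does the requirement for identical procedures fill the gap?** It governs the procedures listed under 8.3.1. Those review medications before the session and record them during it. Giving or holding routine drugs is not among them, so the requirement can be met in full while dose timing differs.

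4. **Do existing safeguards prevent a difference?** Each session has its own pre-dialysis echo, so a drug effect already present at that time is partly absorbed in the session's baseline. An effect that builds or fades over the following 5 hours is not. Appendix 1 marks blood pressure and concomitant medications at baseline, through the session and at 24 hours. These entries can reveal a difference but do not prevent one.

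5. **Is a difference handled in the analysis?** The protocol text does not ask for the time of a dose, and section 9 names no analysis that uses it. The case report form is not in the documents, so it may or may not have such a field.

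Side by side:

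| | Treatment 1 (heparin) | Treatment 2 (SCD) |
|---|---|---|
| Usual drugs continue | Yes | Yes |
| Timing rule for routine drugs | None | After the treatment |
| Medications reviewed and recorded | Yes | Yes |
| Dose time requested in the protocol text | No | No |

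**The case against.** The strongest objection is that only a possibility is shown. For bias to arise, dosing on the heparin day must not already be post-dialysis, the drugs concerned must act on loading conditions, and the shift must alter the change in wall motion over the session. The documents establish none of these. The word used for administration in 7.1 may also cover only drugs given in the unit. All of this stands, and it is why no size is claimed.

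Second, the protocol's terms are not always tidy. Section 6.3.14 speaks of a new SCD cartridge for each treatment, section 10.1 mixes SCD treatment with study hemofiltration treatment, and section 10.2 refers to a first such treatment. So 7.1 may be loosely drafted rather than deliberately limited to one session. That is plausible, but it does not extend the rule to the heparin session. If both sessions were meant, the rewording would only say so.

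Third, the Appendix 1 grid places in-session doses to about the hour, and medications are reviewed beforehand. This is fair: what remains open is mainly the time of a dose taken before the session.

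Fourth, the study calls itself an exploratory pilot with descriptive primary analyses, and order, anticoagulant and dialysate calcium would still differ between sessions. Matching drug timing would not by itself isolate the device effect. Section 9 does, however, plan significance tests between sessions. The other differences come with the chosen design, whereas this one serves no stated purpose.

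**Conclusion.** The concern holds. The plan's only medication-timing rule applies to one of the two sessions being compared, and nothing else in the text requires the other session to match. Any difference that resulted would coincide with treatment in every affected patient and could not be cleanly separated from a device effect.

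No magnitude is supported: the documents do not give the drugs involved, the usual dosing practice, or the direction or size of any effect. The conclusion rests on reading SCD treatment as the single SCD session, which most of the protocol's usage supports. If patients already take their routine drugs after dialysis, the sessions match and nothing is lost. It is a cheap improvement rather than a serious flaw, with medium confidence.

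**What to change.** Reword 7.1 so that each patient's routine medications have the same timing relative to dialysis in Treatment 1 and Treatment 2. One option is to give them after the session and its post-dialysis echo (8.3.1.38) on both days. Keeping each patient's usual timing on both days would also match the sessions, but it would replace the present SCD-day rule. Either way:

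- keep other needed medications allowed at any time;
- state whether the rule covers drugs taken at home as well as those given in the unit;
- note the time of the last dose at the existing review before each session (8.3.1.8);
- report any patient whose timing differed between the two sessions.

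The cost is one sentence and one extra entry at a review that already takes place, with no added visits, staff or patients. The real burden falls under the first option: some patients' drugs would be deferred on the heparin day past a 5-hour session and an echo, which moves that session away from their usual dosing. The investigator should weigh this when choosing between the options.

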8.11 Key Study Measurements

- ❖ Adverse events, vital signs, and laboratory data
- ❖ Regional wall abnormalities and myocardial strain on spectral tracking on echocardiogram (see section 8.4.1)

8.12 Exploratory Measurements

- ❖ Soluble Markers (Elastase, Hs CRP, IL-6, IL-10, TNF- α , L-Selectin, MCP-1, IL-17, IL-23, IL-8, G-CSF, IL-1 β , WBC, platelet count, Neopterin)
- ❖ Leukocyte flow cytometry (circulatory monocyte subsets)
- ❖ SCD integrity monitoring during treatment will include visual inspection for clotting and hemolysis, and additional testing following return of hemofilter to the research laboratory.

8.2 Screening Procedures (See also Appendix 1)

Initial screening of Subjects for eligibility may be performed within 4 weeks prior to the start of treatment. Informed consent should be obtained prior to initiation of any study-specific procedures.

- ❖ Obtain informed consent.
- ❖ Review CBC with Differential and Platelet Count that would fall into the Screening Period window.
- ❖ Review Entry Criteria, including Medical History and Concomitant Medications. If the subject meets the entry criteria, including Concomitant Medications, contact the study monitor to confirm admission to the study.
 - ❖ Perform a pregnancy test on women of child bearing potential (serum quantitative bHCG)

8.3 Hemodialysis Procedures – (See also Appendix 1)

Subjects will enter the Hemodialysis Period within 4 weeks of completing the screening process.

8.3.1 Study Treatment

Each Subject will have the treatments described below, during which identical study procedures will be performed during each study treatment.

Treatment 1: Initial standard hemodialysis treatment with heparin (SHH) anticoagulation.

Treatment 2: A single hemodialysis treatment with SCD treatment and regional citrate anticoagulation one week after Treatment 1.

Each subject's safety data will be monitored by the PI on an ongoing basis.

Prior to start of Study Treatment (SHH or SCD Treatment)

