Treatment Plan	Each Subject will receive one standard study hemodialysis treatment with heparin anticoagulation during which all procedures noted in Appendix 1 will be performed. Subsequently each subject will receive hemodialysis with the added SCD filter anticoagulated with regional citrate.
Data Safety Monitoring	This is a small feasibility study. A safety analysis will be performed on each patient prior to their next hemodialysis treatment by the PI.
Key Measurements	
 ❖ Adverse events ❖ Regional wall abnormalities and myocardial strain on Echocardiogram
Exploratory Measurements	
 ❖ Soluble Markers (Elastase, Hs CRP, IL-6, IL-10, IL-17, IL-23, G-CSF, TNF-α, MCP-1, L-selectin, neopterin, IL-1β, IL-8) ❖ Leukocyte flow cytometry (circulatory monocyte subsets and circulatory activated neutrophils) ❖ WBC and platelet counts

Primary Analyses	Descriptive analysis will be conducted on the following parameters in all Subjects exposed to any study hemodialysis treatment: 
 ❖ Adverse events ❖ Regional wall abnormalities and myocardial strain ❖ Clinical laboratory and physiological measurements
Secondary Analyses	A number of secondary analyses will be conducted, including the following: 
 ❖ Mean change from baseline in cytokines at the end of each treatment ❖ Mean change from baseline in markers of inflammation at the end each treatment
Study Periods and Study Duration	
 ❖ The total duration of participation will be approximately 3 weeks.

1. Background and Rationale

More than 400,000 people are currently treated by hemodialysis (HD) in the US end stage renal disease (ESRD) program. The mortality in this group of patients is unacceptably high with almost half of the deaths due to cardiovascular disease (CVD). Strategies to reduce the mortality of HD patients with directed interventions at cardiovascular risk factors have largely been ineffective. It is well recognized that HD patients suffer excess morbidity and mortality, mainly due to cardiac failure and sudden death rather than traditional thrombotic occlusion leading to acute myocardial infarction (AMI).^{1,2} The excess cardiovascular risk is not the result of the traditional factors associated with CVD but a combination of non-traditional factors unique to chronic kidney disease (CKD).

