5mg/L were enrolled to assess the safety and early efficacy signals on inflammatory biomarkers in these patients. After a Non-Significant Risk designation by the Henry Ford Health System (HFHS) IRB, this study was performed ²¹. The clinical results demonstrated an excellent safety profile with no decline in total WBC, NE or platelet counts. To evaluate the effect of SCD therapy on M phenotypes in these patients, determination of CD14^{hi} fluorescent intensity on peripheral blood M was analyzed utilizing flow cytometry. SCD therapy promoted a shift in MO phenotype from predominantly CD14^{hi} expressing MO at baseline/pre-SCD therapy to CD14^{low} expressing MO post-SCD therapy (Figure 4, A/B). In the 13 ESRD patients evaluated, a significant shift in MO population phenotype afforded by a single SCD therapy session was observed ($p<0.013$). In a subset of patients ($n=7$) presenting with T2D, indicative of an even greater chronic inflammatory state, this persistent decline in M CD14 expression was sustained as long as 2 weeks post therapy (Figure 4, C). The average number of cells bound to the SCD membrane following 4 hours of therapy showed 1.13×10^9 , with 68% identified as NE, 23% M, 7% eosinophils and 0% lymphocytes. The eluted M were almost all of CD14^{high} phenotype; with the differential percentage being more than double the average 9% circulating M pool. Of note, two patients underwent SCD treatment with standard heparin HD (SHH), as opposed to RCA. No change in M phenotype was observed, but symptomatic and biochemical adverse events were seen after SHH+SCD treatment, including a greater than doubling of CRP levels. No further studies were undertaken with SHH+SCD treatment due to these adverse events.

Myocardial stunning in ESRD patients undergoing chronic hemodialysis

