The blood flow path is changed in the second cartridge compared to conventional use, with blood flowing outside the hollow fibers in the extracapillary space of the hemofiltration cartridge. The lumens of the hollow fibers of the second cartridge will be filled with normal saline, and the entry and exit ports will be capped. This formulation is a reversal of conventional fluid flow mechanics of the dialysis membrane. The risk of this change in flow geometry has proven to be minimal. The use of this second cartridge in this extracorporeal perfusion circuit has been evaluated in over 100 large animals in pre-clinical testing and in 123 patients in Phase I, II, and III clinical studies with no unanticipated adverse events related to the second cartridge and the perfusion circuit. These studies have used both systemic heparin and regional citrate anticoagulation treatments. In fact, in the clinical experience, if clotting occurs within the circuit, it has always been initiated in the first dialysis cartridge. The anticoagulation protocols, both systemic heparin and regional citrate in general (see sections 6.3.4 and 6.3.5), are currently established and routinely used in clinical hemodialysis at many medical centers. Potential benefits may be a short-term improvement of the chronic pro-inflammatory state of ESRD.

For our intended use population the following risk are: cardiac arrhythmias, atrial fibrillation, atrial flutter, bradycardia, sinus tachycardia, ventricular fibrillation, ventricular tachycardia. these risks are all associated with myocardial ischemia. This risk is higher in the intended use population since the enrolled patients will have a tendency to myocardial stunning/ischemia promoting intradialytic hypotension.

3. Study Objectives

The objective of the study is to evaluate the efficacy and safety of SCD in diminishing ischemia induced myocardial stunning events observed in ESRD patients on chronic

hemodialysis requiring aggressive ultrafiltration. Our aim is to decrease myocardial stunning events in hemodialysis patients.

4. Study Design

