4.1 Design

This is an exploratory pilot trial. The subject population to be studied are those who have been on chronic hemodialysis for ≥ 3 months with recurrent intradialytic weight gain >0.04 kg/kg body weight.

[figure not shown]
Regional myocardial wall abnormalities and biomarker measurements will be compared pre and post hemodialysis with standard heparin anticoagulated hemodialysis treatment and after one hemodialysis treatments with the regional citrate anticoagulated SCD device.

[figure not shown]
Two different treatment regimens are planned for this clinical trial.

Treatment 1 will be a 5 hour hemodialysis treatment session utilizing heparin anticoagulation. The first hour will utilize a blood flow rate (BFR) of 300 mL/min and a dialysate flow rate (DFR) of 600 mL/min with no ultrafiltration (UF). After the first hour, the blood flow rate will be adjusted to 200 mL/min with a dialysate flow rate of 400 mL/min. This BFR and DFR will be maintained for the remaining 4 hours of the 5 hour session.

Treatment 2 will be a 5 hour hemodialysis treatment session. The first hour will be undertaken with heparin anticoagulation utilizing a BFR of 300 mL/min and a dialysate flow rate of 600 mL/min with no UF. After the first hour, the SCD will be integrated into the circuit with regional citrate anticoagulation and BFR adjusted to 200 mL/min with a DFR of 400 mL/min. This BFR and DFR with RCA will be maintained for the last 4 hours of the 5 hour session.

Of importance, this 5 hour session is planned to ensure adequate solute clearance but with only 4 hour high UF to achieve the patients dry weight.

The hemodialysis treatments will be performed at the Acute Dialysis Unit, University of Michigan.

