8.5 Study Exit Procedures

A Study Termination form will be completed for all patients who have completed the Study Procedures according to the protocol as well as for those who are terminating early for any cause

9. Statistical Considerations

Sample size determination for primary outcome regional wall abnormalities: Our consultant, [name] has previously demonstrated a difference in this variable in 8 to 10 patients using a similar protocol to this proposal when comparing standard and biofeedback dialysis and dialysis cooling ^{33,34}. Sample size of 10 would appear to be sufficient to detect a difference of 20% and is based upon a standard deviation of 14%, significance level of 0.05 and 80% power. In the [name] studies, differences of greater than 20% were observed. We plan to recruit 10 patients in this study, to better ensure an adequate sample size to obtain statistically relevant primary and secondary endpoint comparisons. The patients will serve as their own controls, comparing BL-SHH parameters to SCD therapy parameters. Independent t-test will be used to compare the peak frequency of MS between SHH and SCD sessions. Global LVEF and wall motion in 16 segments in 8 regions at each time point in the dialysis session will be compared using repeated measures and Bonferroni's test for multiple comparisons. IDWG will be compared using paired and unpaired non-parametric testing or t-test if the variable is

normally distributed. These approaches have shown significance in prior studies for MS in HD. Statistical correlations are planned for regional wall abnormalities, inflammatory indices, monocyte subsets and pre-dialysis blood pressures ^{33,34}

10. Adverse Events

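### SCD is always the second session, so order and device effects cannot be separated, yet the plan tests for efficacy without limiting what a difference means

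*Combined protocol and SAP*

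**What the plan says.** The order is the same for all patients. Section 8.3.1 sets Treatment 1 as heparin dialysis and Treatment 2 as "A single hemodialysis treatment with SCD treatment and regional citrate anticoagulation one week after Treatment 1". The synopsis (Treatment Plan) agrees: "Subsequently each subject will receive hemodialysis with the added SCD filter anticoagulated with regional citrate".

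The stated aim includes efficacy. Section 3 reads "The objective of the study is to evaluate the efficacy and safety of SCD in diminishing ischemia induced myocardial stunning events". Section 9 adds "The patients will serve as their own controls, comparing BL-SHH parameters to SCD therapy parameters", gives a powered sample size, and names an independent t-test of peak stunning frequency between the two sessions. Section 8.4.1 says that wall-motion scores before, after and 24 hours after dialysis will be tested between Treatment 1 and Treatment 2.

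Other text points to a more modest claim. Section 4.1 says "This is an exploratory pilot trial". The synopsis calls the trial a small feasibility study and makes its primary analyses descriptive.

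Each session has its own baseline: echo, weight, blood pressure, soluble markers and flow cytometry are taken before both (section 8.3.1, Appendix 1). Section 8.4.1 sets the pre-to-post echo comparison in the standard session against that in the SCD session. The synopsis uses change from baseline for cytokines and inflammation markers. Section 9 also compares interdialytic weight gain (IDWG).

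**The concern.** With a fixed order, anything that differs between a patient's first and second study session falls on the device side of the comparison. No analysis of these data can separate the two.

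The protocol's own background makes one route concrete. Section 1 ties stunning to ultrafiltration load. Sections 6.3.4 and 6.3.15 set net ultrafiltration from that day's weight relative to dry weight, so the load follows the week's weight gain. A lighter load in the second week would look like less stunning on SCD. Section 8.4.1 itself notes that intravascular volume and systolic pressure vary and affect echo parameters.

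What is at stake is the conclusion. A significant between-session test, under an efficacy objective and with no stated limit, would be read as showing that SCD reduces stunning.

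**Working it through.** **Inputs.** From section 9: n = 10, difference 20, SD 14, significance level 0.05, power 80%. The text reads "Sample size of 10 would appear to be sufficient to detect a difference of 20" percent and "is based upon a standard deviation of 14" percent. It does not say whether 14 is a per-session SD or the SD of the within-patient difference, and it does not state sidedness. I take percentage points and a two-sided test, and carry both readings of the SD.

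**The plan's own figure.** Take a paired t-test with per-session SD 14 and uncorrelated sessions. The SD of the difference is 14 × √2 = 19.8, and the noncentrality is 20 / (19.8/√10) = 3.19. Power is 75.6% at n = 9 and 81.1% at n = 10, so 10 reproduces. At n = 10, power is 85.5% for an independent t-test and 97.9% for a paired test with 14 as the SD of the difference. The sample size is not in question here.

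**What a baseline subtraction removes.** Suppose the whole second week shifts by b. The change-versus-change contrast is [(post₂ + b) − (pre₂ + b)] − (post₁ − pre₁), and b cancels. In simulation (SD 14, all correlations 0.5), rejection stayed at about 5% for b = 0, 10 and 20. If b enters only the post-dialysis value, meaning that the response to dialysis has changed, it does not cancel.

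**What drift does where it does not cancel.** The documents give no drift size, so 5 and 10 points (a quarter and a half of the 20-point target) are assumptions. Let b be a favourable drift that enters the contrast in full, with no device effect. The probability of a significant result in the favourable direction is P(T > t₀.₉₇₅), where T is noncentral t:

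- paired test: 9 degrees of freedom, critical value 2.262, noncentrality b / (SD of difference/√10);
- independent test: 18 degrees of freedom, critical value 2.101, noncentrality b / (14 × √(2/10)) for uncorrelated sessions, and simulation for correlated ones.

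| Test | b = 5 | b = 10 |
|---|---|---|
| Paired, SD of difference 14 | 17.2% | 52.2% |
| Paired, SD of difference 19.8 | 10.7% | 29.8% |
| Independent, correlation 0 | 11.4% | 32.7% |
| Independent, correlation 0.25 | 8.7% | 30.7% |
| Independent, correlation 0.5 | 5.7% | 28.2% |
| Independent, correlation 0.75 | 2.6% | 24.5% |

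The nominal rate in that direction is 2.5%. The independent test gives the lower figures because it ignores the pairing and is conservative when sessions are positively correlated. A paired test with correlation 0.75 (SD of difference 14 × √0.5 = 9.9) lies outside this range, at 29.8% and 81.1%.

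**How well ten patients can show drift.** The 95% half-width for a Treatment 2 minus Treatment 1 baseline difference is 2.262 × SD of difference/√10. If SD 14 is assumed for baseline values, this is 14.2, 12.3, 10.0 and 7.1 points at correlations 0, 0.25, 0.5 and 0.75. That is 35–71% of the 20-point target.

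**The case against.** A reader might infer that every week-to-week change is credited to the device. The documents do not support that. The echo comparison in section 8.4.1 and the marker analyses in the synopsis use each session's own baseline, so an additive level shift cancels. Section 1 defines stunning as a transient fall in function, so peak stunning frequency may itself be a within-session measure, although section 9 does not say so.

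Nor are the two baselines wholly unused. Section 8.4.1 tests scores from all three time points between treatments, and section 9 compares ejection fraction and wall motion at each time point. Both can be read to include a pre-dialysis comparison. IDWG bears directly on volume state. None of this is labelled as a check on drift or tied to interpretation.

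The fixed order is also defensible. Section 1 reports a "persistent decline in M CD14 expression was sustained as long as 2 weeks post therapy" in a diabetic subset of the earlier dialysis pilot, and up to 4 weeks of improved myocardial performance in dogs. Both exceed the one-week gap, so swapping the order at that gap would risk carryover. Section 8.3.1 also requires a safety review before SCD. An argument from familiarity with the session is weak: patients have had at least 3 months of thrice-weekly dialysis, and both sessions share length and flow rates.

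These points narrow the exposure but do not remove it. Drift in the response to dialysis survives every planned analysis, and the independent t-test in section 9 states no baseline term.

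**Conclusion.** The point holds in limited form. Order and device are the same variable, efficacy is a stated objective, between-session significance tests are planned, and no passage says that the two effects cannot be separated. The exposure is drift in the response to dialysis in all analyses, plus level drift in the tests for which no baseline term is stated: the independent t-test in section 9 and the between-treatment score comparison in section 8.4.1.

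The size is illustrative: a false benefit in about 3–17% of trials at an assumed 5-point drift and about 24–52% at 10 points, against a nominal 2.5%. This rests on n = 10, full entry of the drift into the contrast, and either a paired SD of difference of 14–19.8 or an independent test with SD 14 and correlation 0–0.75. The documents do not show that drift of this size occurs, and they do not support reading the fixed order as an error in itself. The exploratory and descriptive labels already point to a modest claim; sections 3 and 9 do not match them.

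**What to change.** Keep the fixed order and make two changes.

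1. In sections 3 and 9, define the contrast as second-session SCD with citrate against first-session heparin. State that order and device effects cannot be separated, and that a difference is a signal for a controlled-order trial and not evidence of efficacy. This brings both sections into line with section 4.1 and the synopsis.

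2. In section 9, replace the independent t-test with the within-patient change-versus-change contrast of section 8.4.1. If all correlations are 0.5, its SD is √(4 × 196 × 0.5) = 19.8, so power for 20 points stays at 81.1%. Beside it, report by session, with paired differences and 95% intervals: achieved weight removal (pre minus post weight), IDWG, and pre-dialysis systolic pressure, wall-motion score and GLS. Label this a comparability table that cannot rule out drift. Its pre-dialysis rows cannot detect a changed response to dialysis; weight removal and IDWG bear on that only through volume load. With half-widths of about 7–14 points, a null result there is not reassurance.

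The cost is a weaker claim and one extra table from data already collected. Sessions, visits and sample size do not change.
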